## **DURATION OF RESPONSE**

The DR for CR and PR will be measured from the date that any of these best responses is first recorded until the first date that PD is objectively documented. DR will be summarized using descriptive statistics (N, mean, standard deviation, median, minimum, and maximum) as well as categorically. For patients who continue treatment post-progression, the first date of progression will be used for the analysis.

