# 4.2.2 Secondary Endpoints

- ORR, and DR, according to RECIST Version 1.1 as determined by investigator review, and OS
- invPFS, ORR, DR, and OS in patients with baseline T790M mutations confirmed by central EGFR mutation assay
- Change from baseline in QOL as measured using the PRO of EORTC QLQ-C30, EORTC QLQ-LC13, the DLQI, and the EQ-5D following treatment with CO-1686 versus erlotinib
- Treatment-emergent AEs, laboratory abnormalities and ECG abnormalities
- Plasma PK parameters for CO-1686 based on sparse sampling

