#### 11.2 Statistical Methods

#### 11.2.1 General Considerations

Quantitative variables will be summarized using descriptive statistics (N, mean, standard deviation, median, minimum, and maximum) and/or frequency and percentages for medically relevant categories. Categorical variables will be presented using frequencies and percentages.

Kaplan-Meier methodology will be used to summarize time-to-event variables. The number of patients with events and the number of censored patients will also be presented. The stratified logrank test will be used to compare the time-to-event distributions between the randomized treatment groups. The same variables used to stratify the randomization will be used in the stratified analyses. In addition, the Cox proportional hazards model will be used to estimate the HR between the randomized treatment groups.

The Fisher's Exact Test will be used to compare frequencies between treatment groups and the t-test will be used for comparing means between treatment groups.

All data will be used to their maximum possible extent but without any imputations for missing data. Results from Phase 2 and Phase 3 will be presented separately and pooled.

All statistical analyses will be conducted with the statistical analysis software (SAS®) system, Version 9.1 or higher.

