#### 11.2.4.1 Primary Endpoint

The primary endpoint of the study is invPFS.

invPFS will be calculated as 1+ the number of days from the date of randomization to disease progression, as determined by the investigator or death due to any cause, whichever occurs first. Patients without a documented event of progression will be censored on the date of their last adequate tumor assessment (i.e., radiologic assessment) or date of randomization if no tumor assessments have been performed.

Kaplan-Meier methodology will be used to summarize invPFS. The stratified logrank and the HR will be used for comparing the invPFS distributions among the CO-1686 and erlotinib-treated patients. The invPFS analysis will be stratified by EGFR mutation status (L858R, exon 19 deletion, or other) and territory of residence at time of randomization (Asia vs non-Asia). If the exon 19 deletion subgroup or other mutation subgroup has fewer than 30 patients than these subgroups will be combined for this analysis.

A PFS sensitivity analysis based on an independent radiographic review (irrPFS) will be performed. The irrPFS is defined as the time from randomization to disease progression according to RECIST v1.1 as assessed by independent radiographic review, or death due to any cause, whichever occurs first.

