# **Duration of Overall Response**

The duration of overall response is measured from the time measurement criteria are met for CR or PR (whichever is first recorded) until the first date that recurrent or PD is objectively documented (taking as reference for PD the smallest measurements recorded since the treatment started).

The duration of overall CR is measured from the time measurement criteria are first met for CR until the first date that recurrent disease is objectively documented.

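### Duration of response is undefined for responders who die without documented progression or are still in response, and it is biased in opposite directions depending on how the gap is filled

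*Combined protocol and SAP*

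**What the plan says.** DR is a secondary endpoint (Section 4.2.2: "ORR, and DR, according to RECIST Version 1.1 as determined by investigator review, and OS"), and Section 4.1.2 makes its comparison between arms a secondary objective.

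- **End of DR.** Under Section 11.2.4.2, DR runs from the date a CR or PR "is first recorded until the first date that PD is objectively documented". Appendix A (Duration of Overall Response) likewise runs "until the first date that recurrent or PD is objectively documented". Neither names death.
- **Summary of DR.** Section 11.2.4.2 states: "DR will be summarized using descriptive statistics (N, mean, standard deviation, median, minimum, and maximum) as well as categorically". It adds a rule for patients treated beyond progression, but none for responders who die, remain in response or are lost to follow-up.
- **General rules.** Section 11.2.1 says "Kaplan-Meier methodology will be used to summarize time-to-event variables", without naming DR, and "All data will be used to their maximum possible extent but without any imputations for missing data".
- **invPFS.** Section 11.2.4.1 ends invPFS at progression "as determined by the investigator or death due to any cause, whichever occurs first". Its next sentence reads: "Patients without a documented event of progression will be censored on the date of their last adequate tumor assessment", with the randomization date used if there was no assessment.

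**The concern.** A responder who dies before PD is documented has an end date for invPFS but none for DR. A responder still in response at the cutoff has no DR end date either, and the DR text does not say that such a patient is censored. Whoever programs the analysis must choose whether to censor these patients, drop them, or enter their observed time as if complete, possibly after seeing the data. The choices give different answers, and not in the same direction.

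DR is meant to be compared between arms. If deaths without PD, or the share of responses still ongoing, differ between CO-1686 and erlotinib, an unstated handling rule can create or hide a difference in DR. Section 11.2.1 also leaves the comparison open: it gives the logrank test for time-to-event variables and the t-test for means, and the DR text plans a mean and SD.

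**Working it through.** **1. The plan's own figure.** The only power statement (Section 11.3) concerns PFS: 640 events, about 80% power, HR 0.80, one-sided 0.025, 1:1 allocation.

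- Schoenfeld: 4 × (1.960 + 0.842)² / (ln 0.80)² = 631 events.
- Freedman: (1.80/0.20)² × (1.960 + 0.842)² = 636 events.
- Power at 640 events: 80.6%.

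The figure reproduces. DR has no sample size, power or expected value, so the rest is illustration.

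**2. Assumptions, none of them from the documents.** The true time from response to PD or death is exponential with median 10 months, so λ = ln 2 / 10 = 0.0693 per month. A share d of endings are deaths without PD, with d from 2% to 15%. Follow-up after response is uniform over 6 to 24 or over 12 to 36 months.

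**3. Reading A: Kaplan-Meier with deaths censored.** The hazard of PD alone is (1 − d)λ, so the estimated median is ln 2 / [(1 − d)λ] = 10 / (1 − d).

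| d | 10 / (1 − d), months | Simulated, months |
|---|---|---|
| 2% | 10.20 | 10.19 |
| 5% | 10.53 | 10.52 |
| 10% | 11.11 | 11.14 |
| 15% | 11.76 | 11.78 |

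The simulation used 400,000 responders. With death as an event it returns 9.97 to 10.02 months. Reading A therefore overestimates the median by 2% to 18%.

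**4. Reading B: descriptive summary of responders with a PD date.** The share of responses that end before the cutoff is 1 − (e^(−aλ) − e^(−bλ)) / [(b − a)λ], for follow-up uniform from a to b.

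- 6 to 24 months: 1 − (0.6598 − 0.1895)/1.2477 = 0.623. Half is 0.3115. Solving 1 − e^(−λt) = 0.3115 gives t = 5.4 months.
- 12 to 36 months: 1 − (0.4353 − 0.0825)/1.6636 = 0.788. Half is 0.3940, which gives t = 7.2 months.

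Both solutions lie below the minimum follow-up, so the cutoff does not distort that part of the curve. The simulation agrees (5.39, and 7.22 to 7.24). Simulated means are about 6.5 and 8.8 months, against a true mean of 10 / ln 2 = 14.4.

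**5. What drives Reading B.** Adding deaths as completed durations moves the median by at most 0.01 month. Under constant hazards, deaths and PDs have the same distribution of timing, so the shortfall comes from dropping ongoing responders, who tend to have the longest durations.

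**6. Reading C: every responder's observed time entered as complete.** The simulated median is about 8.2 months (6 to 24) or 10.0 (12 to 36). The mean is about 9.0 or 11.4, still below 14.4.

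**The case against.** The strongest reply is that the DR definition is consistent within the protocol. Section 11.2.4.2 and Appendix A both end DR at PD, and DR need not share an event definition with PFS. That consistency is real, but it does not supply a duration for a responder without a PD date.

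Deaths without documented PD should also be limited by design. Suspected clinical progression needs CT or MRI confirmation (Section 5.1.2), patients who stop treatment without PD are still scanned every 8 ± 1 weeks (Sections 5.1.4 and 9.5), and Appendix A asks for progression to be documented even after treatment stops. This argues for the lower end of the range for d. It does nothing for ongoing responders.

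DR also carries no alpha or power, its own paragraph names no between-arm test, and the current amendment ends development and closes enrollment (Appendix D). This limits the weight of the point. However, Section 11 is still current text and a clinical study report is planned (Section 13.9).

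A reader might take the deaths in Study CO-1686-008 as an estimate of d, since 3 of 11 on-study or 28-day deaths were not due to progression (Section 3.2.1). They do not support that. They are a share of deaths among 148 previously treated patients, not a share of response endings. They are not restricted to responders, one was of unknown cause, and all 11 were assessed as unrelated to study drug.

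**Conclusion.** The gap is real: responders without a PD date have no defined DR, and two natural ways of filling the gap bias the result. Censoring deaths in a Kaplan-Meier analysis lengthens the median to 10.5, 11.1 or 11.8 months for d = 5%, 10% or 15%. Limiting the descriptive summary to responders with a PD date shortens it to 5.4 or 7.2 months. Both compare with an assumed true 10 months and rest on constant hazards and the assumed follow-up.

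A reader might infer that the plan simply overestimates DR because it ignores death. The documents do not support that. Overestimation needs Kaplan-Meier with deaths censored, and the DR paragraph specifies neither. On its own descriptive wording, the likelier error is the opposite one, and missing censoring matters more than missing deaths. Nor do the documents show which arm would gain, because they give no rate of death without PD by arm.

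A reader might also infer that invPFS censors deaths, because its censoring sentence mentions only progression. The definition just before it counts death as an event, so this is a wording conflict to remove and not evidence of a different primary endpoint. The 640-event calculation stands. The point should be fixed, but it concerns a secondary endpoint only.

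**What to change.** 1. In Section 11.2.4.2, define DR as the time from first recorded CR or PR to first documented PD or death from any cause, whichever occurs first.
2. Censor all other responders at their last adequate tumor assessment.
3. Summarise DR by Kaplan-Meier (median with confidence interval, numbers of events and censored patients) in place of the mean and SD.
4. In Section 11.2.4.1, apply the censoring sentence to patients without documented progression or death, so that the two endpoints treat deaths alike.
5. State that the Section 11 definition governs the analysis where Appendix A differs.

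Steps 1 to 3 belong together: adding death alone would leave the descriptive median almost unchanged.

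The cost is a few sentences and no new data collection, because main-study follow-up already records scans to progression and survival (Sections 5.1.4 and 9.5). Under Appendix D, participation ends after the End-of-Treatment Visit, so extension patients leaving without PD or a recorded death would be censored. The reported median DR may differ from the one the current text would give, and the direction depends on which reading would have been used.

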# 4.1.2 Secondary Objectives

- To compare secondary measures of clinical efficacy (ORR, DR, and OS) of oral single-agent CO-1686 with that of erlotinib when administered as a first-line targeted treatment in patients with advanced/metastatic NSCLC whose tumors have EGFR-activating mutations
- To assess PFS, ORR, DR, and OS in patients with baseline T790M mutations based on central allele-specific polymerase chain reaction (PCR) EGFR mutation assay
- To assess quality of life (QOL) using the patient-reported outcomes (PRO) of European Organization for Research and Treatment of Cancer Core Quality of Life Questionnaire (EORTC QLQ-C30) and the EORTC Quality of Life Questionnaire Lung Cancer module (EORTC QLQ-LC13), 15 the Dermatology Life Quality Index (DLQI), 16 and the EQ-5D instrument 17 in patients receiving treatment with CO-1686 versus erlotinib
- To evaluate safety and tolerability of CO-1686 versus erlotinib in patients with advanced/metastatic NSCLC whose tumors have EGFR-activating mutations
- To determine PK of CO-1686 in this patient population using population PK (POPPK) methods and explore correlations between PK, exposure, response, and/or safety findings

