## PATIENT REPORTED OUTCOMES (QUALITY OF LIFE)

QOL will be measured using the PROs of EORTC QLQ-C30, EORTC QLQ-LC13, the DLQI, and the EQ-5D. 15-17

The EORTC questionnaires will be scored using the published scoring algorithms provided by the EORTC. For each item or scale, a linear transformation will be applied to standardize the raw score to a range from 0 to 100. A high scale score represents a higher response level.

Thus a **high score for a functional scale** represents a *high / healthy level of functioning*, a **high score for the global health status / QOL** represents a *high QOL*, but a **high score for a symptom scale / item** represents a *high level of symptomatology / problems*.

The baseline PRO measurement will be defined as the last value prior to or on the day of the first dose of CO-1686 or erlotinib. The on-treatment period will be defined as the day after the first dose of CO-1686 or erlotinib to 28 days after the last dose of protocol-specified treatment. QOL measurements collected during the on-treatment period will be included in the summary tables.

The summary of PRO data will include descriptive statistics (N, mean, standard deviation, minimum, median, and maximum) of the observed measurements at each visit during the on-treatment period. Summaries using descriptive statistics of the change or percent change from baseline to each visit during the on-treatment period may also be provided. Graphical presentations may be used to present the mean changes over time.

The time to a worsening in symptoms will be computed as 1+ the number of days from the date of randomization to the first instance of  $a \ge 10$  point increase from baseline in symptoms. Patients without an event will be censored on the date of their last assessment. Kaplan-Meier methodology will be used to summarize the time deterioration and the treatment groups will be compared using the logrank test and hazard ratio.

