#### **OVERALL SURVIVAL**

OS will be calculated as 1+ the number of days from the first dose of study drug to death due to any cause. Patients without a documented date of death will be censored on the date the patient was last known to be alive.

Kaplan-Meier methodology will be used to summarize OS and the treatment groups will be compared using the logrank test.

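### Duration of response is given mean, SD and median as if every response had ended, with no censoring date, against the plan's own Kaplan-Meier rule

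*Combined protocol and SAP*

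**What the plan says.** Section 11.2.4.2 starts DR at the first record of CR or PR and runs it "until the first date that PD is objectively documented". The next sentence gives the method: "DR will be summarized using descriptive statistics (N, mean, standard deviation, median, minimum, and maximum) as well as categorically". The only other rule there is that patients treated beyond progression use their first progression date, which is an event rule. Appendix A (Duration of Overall Response) repeats the start and end and adds no censoring date. Neither place mentions death without documented progression.

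The general rule in section 11.2.1, also in the Synopsis, is: "Kaplan-Meier methodology will be used to summarize time-to-event variables". Section 11.2.1 adds: "The number of patients with events and the number of censored patients will also be presented". It assigns the list of statistics used for DR to quantitative variables, and it excludes imputation of missing data.

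Section 4.1.2 makes DR part of a between-arm objective: "To compare secondary measures of clinical efficacy (ORR, DR, and OS) of oral single-agent CO-1686 with that of erlotinib".

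**The concern.** A responder still in response at data cutoff has a duration known only to exceed what has been seen. A mean, SD or sample median has no place for such a patient. A programmer working from section 11.2.4.2 has three options:

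1. **PD only.** Use only responders with documented progression. The no-imputation rule makes this a natural choice, since the others have no end date. It selects the shorter durations.
2. **Ongoing as complete.** Enter each ongoing duration as if it had ended.
3. **Kaplan-Meier.** Apply section 11.2.1 and add the listed statistics alongside. No censoring date is supplied with which to do it.

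The reported DR for each arm, and the apparent difference between arms, would depend on a choice the plan does not make.

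**Working it through.** **Endpoints side by side**

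| Endpoint | Method named | Censoring date |
|---|---|---|
| Investigator PFS (11.2.4.1) | Kaplan-Meier | "Patients without a documented event of progression will be censored on the date of their last adequate tumor assessment" |
| Time to symptom worsening (11.2.4.2) | Kaplan-Meier | "Patients without an event will be censored on the date of their last assessment" |
| OS (11.2.4.2) | Kaplan-Meier | "Patients without a documented date of death will be censored on the date the patient was last known to be alive" |
| PFS by independent review (11.2.4.1) | none of its own | none |
| Plasma mutant-EGFR times (11.2.6.3) | Kaplan-Meier | none |
| DR (11.2.4.2, Appendix A) | mean, SD, median etc. | none |

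**The plan's own figure.** No figure is given for DR. The sample-size figure reproduces: events = 4(1.960 + 0.842)² / (ln 0.80)² = 631, and 640 events give power Φ(√640 × 0.2231/2 − 1.960) = 80.6%, against the stated 80%. Nothing here disputes it.

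**Inputs for the illustration.** From section 11.3: erlotinib median PFS 10 months and HR 0.80, so 10/0.80 = 12.5 months on CO-1686. Assumed: exponential PFS, every PFS event counted as progression, first response at 56 days (the first 8-weekly scan), and uniform accrual over 12, 24 or 36 months. DR is then PFS minus 56 days. True DR medians are 10.0 and 12.5. True means are median/ln 2 = 14.4 and 18.0.

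**Hand check at 70% PFS events.** In simulation about 30% of erlotinib and 37–38% of CO-1686 responders have no progression at that point.

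- *Mean, ongoing as complete.* For an exponential time with mean μ, followed exactly to cutoff, the expected observed duration is μ × (share with an event): 14.4 × 0.70 = 10.1 and 18.0 × 0.625 = 11.3.
- *Median, PD only.* With equal follow-up and a share p progressed, the median is −μ ln(1 − p/2): −14.4 × ln(0.65) = 6.2 and −18.0 × ln(0.6875) = 6.7.

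**Simulation at 70% PFS events** (range over the three accrual periods, in months; ongoing responses stopped at the last 8-weekly scan)

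| Quantity | Erlotinib | CO-1686 |
|---|---|---|
| True median | 10.0 | 12.5 |
| PD-only median | 6.2–6.4 | 6.7–7.1 |
| Ongoing-as-complete median | 7.4–10.0 | 9.0–11.2 |
| Kaplan-Meier median | 9.8–10.0 | 12.2–12.4 |
| True mean | 14.4 | 18.0 |
| PD-only mean | 7.3–8.4 | 7.7–9.2 |
| Ongoing-as-complete mean | 9.8–9.9 | 10.9–11.0 |

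The PD-only median is 36–38% low on erlotinib (3.6/10 to 3.8/10) and 43–46% low on CO-1686 (5.4/12.5 to 5.8/12.5). The true 2.5-month gap becomes about 0.5–0.7.

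**Timing of censoring.** The table uses exact progression dates but cuts ongoing durations back to a scan, which deepens the ongoing-as-complete shortfall. With both timed exactly, the CO-1686 median is 9.1–12.2 rather than 9.0–11.2.

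**Maturity.** At 90% PFS events the PD-only medians are still 8.8 and 10.2. The ongoing-as-complete medians are essentially at the true values, but the means remain 13.1–13.3 and 15.3–15.5, which is 8–9% and 14–15% low.

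**Using the plan's 13 months for CO-1686 instead of 12.5.** At 70% events with 24-month accrual, the PD-only medians are 6.3 and 7.0. Ongoing-as-complete gives 9.0 and 10.5. Kaplan-Meier returns 10.0 and 13.0.

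**The case against.** The best reply is that section 11.2.1 already covers DR. Its Kaplan-Meier rule has no exceptions, DR is plainly a time to event, and the list in 11.2.4.2 may be meant as an addition. The plan also says only median, so an ordinary sample median is an inference. This stands in part: Kaplan-Meier is a permissible reading and gives an essentially correct median. It does not settle the matter, because the endpoint-specific sentence names other statistics and neither DR definition supplies a censoring date.

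On importance, 11.2.4.2 names no test for DR, and the amendment says some data will no longer be analysed. But DR is still a secondary endpoint in section 4.2.2, section 11 is unchanged on it, and section 13.9 still plans a clinical study report.

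A reader might infer more than the documents support:

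- *That DR alone lacks a censoring rule.* The independent-review PFS and the plasma mutant-EGFR times lack one too.
- *That the error always pulls the arms together.* That follows from the assumed model. If follow-up ends differently by arm, the direction is not guaranteed.
- *That the illustrated sizes are forecasts.* The 70% rule in section 11.4 governs Phase 3 only, maturity at reporting is not stated, and the model counts deaths as progression although DR as defined ends only at progression.
- *That the Extension Phase leaves many responders with no progression date.* Appendix D requires no scan at the End-of-Treatment visit and leaves scanning after an early stop to the physician. On-treatment scans continue, however, and no count of affected responders is given.

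**Conclusion.** The point holds and should be fixed before DR is reported. A right-censored endpoint carries a summary suited to complete data, against the plan's general rule and without the censoring date that investigator PFS, symptom worsening and OS each have.

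The firm part needs little modelling: while responses are ongoing, the plain mean is too low under either naive option, and the PD-only median is too low. The sizes are illustrative and rest on the exponential, response-time, accrual and progression-only assumptions listed above. The ongoing-as-complete median is less predictable. It runs from unbiased to roughly 20–30% low, depending on accrual, maturity and how censoring is timed. Under these assumptions the gap between arms usually shrinks.

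The primary PFS analysis and the 640-event calculation are untouched. The silence on death without documented progression is a gap in the definition, and no bias is claimed from it.

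**What to change.** In section 11.2.4.2, replace the descriptive-statistics sentence with: *DR will be summarised by Kaplan-Meier (median and 95% CI by arm); responders without an event are censored at the last adequate tumour assessment, as for invPFS.*

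In addition:

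- Do not report a plain mean and SD of DR while responses are ongoing.
- Base any categorical summary on Kaplan-Meier estimates at fixed times, for example 6 and 12 months.
- State, in the same terms in section 11.2.4.2 and Appendix A, whether death without documented progression is an event.

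The cost is one paragraph, plus a matching line in Appendix A if death is made an event. It uses dates already recorded. It cannot recover progression or death dates that were not collected; those responders are censored at their last adequate assessment.
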